#### 4.5 Study Schema

#### 4.6 Outcome Measures

##### 4.6.1 Primary Study Endpoint

Occurrence of all-cause hospital readmissions or death within 60 days of randomization

##### 4.6.2 Secondary Study Endpoints

- Time to readmission or death
- Number of hospital readmissions or ER visits (visits without admissions)

- All-cause mortality

#### **4.6.3 Exploratory Outcomes**

- Change in self-care score at baseline and at end of study in both groups
- NYHA functional class at baseline and at end of study in both groups
- 6 minute walk results at baseline and at end of study in both groups
- Quality of life scores (Minnesota Living with HF) at baseline and at end of study in both groups
- Correlation of data obtained from the BodyGuardian® remote monitoring platform with clinical outcomes

#### **4.6.4 Primary Safety Endpoints**

- All cases of skin irritation requiring prescription treatment and/or withdrawal from the study will be documented
- All Serious Adverse Device Events (SADE) and Unexpected Adverse Device Events (UADE) will be documented and reported according to IRB and federal guidelines.

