## 2.3 *Preliminary Data*

Studies have been completed to evaluate the BodyGuardian® (BG) system in healthy elderly subjects and to test the usability from a subject's perspective and from a clinician's perspective.

In one study, twenty subjects were enrolled; 19 subjects completed the study and 1 withdrew because he could not manage to use the device. The 18 subjects were monitored for 22 days on average (in 21.7 days monitoring exceeded 80% of the day). Six subjects stopped wearing the BG monitor after less than 30 days due to: skin irritation (1); difficulty using/placing the monitor (4); or reluctance to use it due to aches and pains unrelated to the monitoring system (1). An evaluation was done on the ECG signal,

arrhythmia classification algorithm, respiration signal, accelerometer data, and the reliability of wireless connection with the BP cuff and scale. Heart rate data was obtained 99.2% of the time (91.4% reliable); respiration data was obtained 53.9% of the time. Weight and blood pressure were captured 75.7% and 74.0% of the time, respectively.

Since many HF patients have pacemakers and implantable cardiac defibrillators (ICDs), the system was evaluated for electromagnetic interference (EMI) with these devices. The BodyGuardian® module and adhesive electrode strip was applied to the skin directly over the implanted device in 100 subjects. In 208 successful acquisitions and transmissions of electrocardiograms, no EMI was detected (see Appendix 15.14 ICD Interference Letter and Abstract – [name]).

[figure not shown]
[figure not shown]

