### **2.4.2 BodyGuardian® Risks**

The BodyGuardian® is a Class II FDA cleared device for ambulatory monitoring of non-lethal arrhythmias. As a Class II ECG device, it has been classified as a Non-Significant Risk device that is not implantable, does not sustain human life, does not actively treat or cure disease, and does not pose a serious risk to the health and safety of the patient. In the context of this trial as described below, the BodyGuardian® Device and the Patient Care Platform will acquire physiologic data and provide individualized physician-prescribed automated alerts based on physician-prescribed thresholds. These alerts will then be reviewed by the appropriate medical staff as defined in the care protocols and within the scope of practice of the medical staff. This design uses the BodyGuardian® to acquire data and present to the medical staff data they have asked to review based on individual prescriptions for each patient. This design of a Class II device presenting relevant information to medical staff to review and confirm within their scope of practice is consistent with a Non-Significant Risk Device Study.

The BodyGuardian® is being used in this study consistent with its indications for use to remotely monitor ambulatory, non-lethal arrhythmias. The risk of direct harm to a subject using the BodyGuardian® as an external sensor is minimal. As part of the 510 K submission, the FDA reviewed a comprehensive hazard analysis and risk mitigation strategy. The most common potential adverse event is skin irritation or reaction to the adhesive on the SnapStrip™. This will be monitored for all subjects.

Skin irritation: Skin irritation may result from the SnapStrip™ adhesive. For ease in removal, subjects will be instructed to use a warm, damp cloth to soften the edges of the SnapStrip™ before slowly peeling back and rolling the adhesive away from the chest. Subjects should not rip or tear off the SnapStrip™ quickly and the SnapStrip™ should not be attached to broken, damaged, or irritated skin.

Delay in identifying or responding to an abnormal clinical finding. Subjects will be reminded that if they are having worrisome symptoms they should not rely on the BG platform, but rather contact their primary healthcare provider or if necessary, visit the emergency room (ER).

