#### Study Withdrawal

If the subject dies after being randomized but prior to hospital dismissal, the subject will be withdrawn from the study.

If the subject is lost to follow up, every effort will be made to contact the subject and determine the reason that will then be documented, including the measures taken to follow-up. If subject withdraws or drops out of the study, the reason for withdrawal from the study is to be documented on the case report form (CRF) and in the source document. The study coordinator or investigator must attempt to document re-hospitalization data unless the subject expressly refuses to provide this information.

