#### Treatment discontinuation

Subjects who terminate the use of the BodyGuardian® device will continue to be followed. Interruption of the BodyGuardian® device will not be considered treatment discontinuation.

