### **8.5     *Recording of Adverse Events***

At each contact with the subject, the investigator must seek information on study-related adverse events by specific questioning and, as appropriate, by examination. Study subjects will be routinely questioned about study-related adverse effects at study visits. Information on all study-related adverse events should be recorded immediately in the source document, and also in the appropriate adverse event section of the case report form (CRF). All clearly related signs, symptoms, and abnormal diagnostic, laboratory, or procedure results should be recorded in the source document.

All study-related adverse events occurring during the study period must be recorded. All observed or volunteered adverse effects (serious or non-serious) and abnormal test findings, regardless of the treatment group if applicable or suspected causal relationship to the investigational device or if applicable other study treatment or diagnostic product(s) will be recorded in the subjects' case history. For all adverse effects sufficient information will be pursued and/or obtained as to permit: an adequate determination of the outcome; an assessment of the causal relationship between the adverse effect and the

investigational device; or if applicable other study treatment or diagnostic product. The clinical course of each study-related event should be followed until resolution, stabilization, or until it has been ultimately determined that the study treatment or participation is not the probable cause. Serious adverse events that are still ongoing at the end of the study period must be followed up to determine the final outcome. Any serious adverse event that occurs after the study period and is considered to be at least possibly related to the study treatment or study participation should be recorded and reported immediately.

The Adverse Event CRF shall include the following information:

- Subject Study Number/Identifier
- Device information (BG kit and serial number)
- Date of event onset
- Date investigator became aware of event
- Description of the event
- Description of treatment the subject received as a result of the event
- Indication if study treatment was discontinued or if investigational device was removed
- Subject's current status or if the event was resolved
- Date of resolution
- Investigator assessment of the event and justification for determination

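### The primary safety endpoint in 4.6.4 leaves out a permanent BodyGuardian® stop for skin irritation when no prescription is given and the patient stays in the study

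*Combined protocol and SAP*

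**What the plan says.** All references are to the combined protocol and SAP.

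- **Endpoint (4.6.4).** "All cases of skin irritation requiring prescription treatment and/or withdrawal from the study will be documented". The only other item in that section covers serious or unexpected device events.
- **Leaving the study (5.3, Study Withdrawal).** "If subject withdraws or drops out of the study, the reason for withdrawal from the study is to be documented on the case report form".
- **Stopping the device (5.3, Treatment discontinuation).** "Subjects who terminate the use of the BodyGuardian® device will continue to be followed". The next sentence adds: "Interruption of the BodyGuardian® device will not be considered treatment discontinuation".
- **Expected harm (2.4.2).** "The most common potential adverse event is skin irritation or reaction to the adhesive on the SnapStrip™. This will be monitored for all subjects".
- **Recording (8.0 and 8.5).** All study-related adverse events go on a case report form, including those below the level of an unanticipated device effect. The listed fields of the adverse event form include: "Indication if study treatment was discontinued or if investigational device was removed".
- **Analysis (Section 7).** No analysis of the safety endpoint or of the adverse event records is named. Section 7.2.1 has only a general statement that variables will be described.

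**The concern.** The second trigger in 4.6.4 is tied to leaving the study. For a wearable patch, an obvious patient response to irritation is to stop wearing it, and the protocol deliberately keeps such a patient in follow-up. That is right for the readmission endpoint. It also means that the trigger does not respond to a device stop as such.

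What is at stake is how a reader will understand the reported figure. A rate headed as the primary safety endpoint for skin irritation will be taken as the share of patients with irritation bad enough to matter. A patient who could not continue with the device because of irritation belongs in that share on any ordinary reading, but is left out unless a prescription was written or the patient also left the study.

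**Working it through.** The plan gives no target rate, threshold or sample size for this endpoint, so there is no figure to reproduce. The check is mainly a comparison of texts.

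**Step 1: apply the definition.** A patient with irritation is a case if (prescription) or (left the study). Under 5.3, stopping the device does not imply leaving the study. The possible patterns are:

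| Patient with irritation | Prescription | Left study | Case under 4.6.4 | On adverse event form |
|---|---|---|---|---|
| Keeps the device | yes | no | yes | yes |
| Stops for good | yes | no | yes | yes |
| Stops for good | no | yes | yes | yes |
| Stops for good | no | no | **no** | yes, with removal noted |
| Removes it for a time | no | no | no | yes, with removal noted |

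The fourth row is the gap.

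**Step 2: see whether the other safety item covers it.** That item is limited to serious or unexpected device events. Irritation is described in 2.4.2, and Section 8.0 treats effects listed in 2.4 as anticipated. A non-serious case in the fourth row does not enter that way.

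**Step 3: see whether the pattern has occurred.** In the first study of Section 2.3, 20 subjects enrolled, 19 completed and 1 withdrew because he could not manage the device. Six stopped wearing the monitor before 30 days: 1 for irritation, 4 for difficulty and 1 for unrelated aches (1 + 4 + 1 = 6). The single withdrawal had another cause, so the irritation stop was not a withdrawal. Under 4.6.4 it would count only if a prescription was given, and the document does not say.

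**Step 4: scale, as illustration only.** Section 2.3 gives both 20 enrolled and 18 monitored, so both denominators are shown. Limits are exact (Clopper-Pearson): lower = 2.5% quantile of Beta(x, n − x + 1), upper = 97.5% quantile of Beta(x + 1, n − x), with x = 1.

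- n = 20: 1/20 = 5.0%, limits 0.1% to 24.9%.
- n = 18: 1/18 = 5.6%, limits 0.1% to 27.3%.

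With the 4:1 allocation of Section 4.2, the number on the device is 304 × 4/5 = 243.

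- 243 × 5.0% = 12.2 (limits 0.3 to 60.4).
- 243 × 5.6% = 13.5 (limits 0.3 to 66.3).

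Section 7.1 instead plans 152 per group, which gives 7.6 (0.2 to 37.8) or 8.4 (0.2 to 41.5).

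These are *all* stops for irritation. The number missed is stops × u, where u is the share with no prescription who also stay in the study. The documents give nothing on u, so it can lie anywhere from 0 to 1, and the number missed runs from zero to the full count of stops.

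**The case against.** The strongest reply is that nothing is lost. Irritation is to be monitored in everyone, investigators must ask about study-related events at each contact, non-serious effects are recorded, the form notes device removal, and patients who stop the device stay under observation. Section 4.6.4 then only picks out the more severe cases, and setting a severity threshold is a legitimate choice. No hypothesis, threshold or stopping rule depends on it. The case report forms, the safety monitoring plan and the skin irritation guidance (Appendices 15.3, 15.4 and 15.11) appear only as titles and may say more.

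Most of this stands, and it limits the point to the endpoint definition. It does not remove it. The records allow the count to be recovered, but no section defines that count in advance. A severity threshold that includes study withdrawal but not permanent loss of the device is hard to defend as intended.

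A reader might infer more than the documents support:

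- *That these events go unrecorded or unreported.* Section 8.0 does exempt expected and non-serious clinical events from reporting, but it distinguishes these from anticipated device effects. Section 2.4.4 describes expected clinical events as related to heart failure, and irritation is listed as a device risk.
- *That the withdrawal trigger almost never operates.* Some patients may stop the device and also leave, and the reason is then recorded.
- *That this endpoint is the main source of tolerability data.* Section 7.2.4 defines daily wear adherence, and the adverse event form captures irritation. Adherence does not, however, give the reason for stopping.
- *That average wear of 22 and 25 days in earlier studies shows trouble at 60 days.* The 25-day figure comes from a study of recurrence within thirty days, and the other study reports stops before 30 days. Both averages probably reflect short monitoring periods.
- *That 12 to 14 cases will be missed.* That figure rests on one event and counts all stops.

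**Conclusion.** The point holds as a gap in the definition. As written, 4.6.4 excludes a permanent device stop for irritation when there is no prescription and no study withdrawal, although the event is on the adverse event form. Compared with a definition that includes such stops, the reported rate can only be equal or lower. The size of the understatement cannot be determined from the documents: one stop among 18 to 20 pilot subjects, with unknown prescription status, does not support an estimate.

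The conclusion rests on reading withdrawal from the study in 4.6.4 in the sense used in 5.3, and on the appendices not redefining it. It has no bearing on the readmission analysis, the type I error rate or the sample size. It is worth correcting because the correction is cheap and concerns the harm that the protocol itself expects most often.

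**What to change.** In 4.6.4, add *permanent discontinuation of the BodyGuardian® because of skin irritation* as a third trigger beside prescription treatment and study withdrawal. Take it from the device-removal field on the adverse event form (8.5), and report the number and proportion among Tele-HC patients fitted with the device.

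Do not add temporary removals to the endpoint. Section 2.4.2 says that the strip should not go on irritated skin, so almost any irritation could lead to a short removal, and the endpoint would drift towards any irritation at all. A separate descriptive count of temporary removals for irritation is enough.

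The cost is one sentence and one table. The field as listed in 8.5 does not say whether removal was permanent or temporary. If the form does not either, one further tick box is needed. The stated irritation rate becomes somewhat less favourable. No change to the treatment of irritation or to the efficacy analysis is proposed.

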### **4.7 *Questionnaire Tools***

#### **4.7.1 Assessment of Depression and Adherence Tool**

In order to assess adherence in future users, each subject will be asked to complete a baseline depression assessment survey (PHQ-9) and a demographic survey. If a PHQ-9 score indicates a more than minimal severity, standard of care treatment for depression will be followed.

#### **4.7.2 Self-Care and Life Quality Evaluation**

Each subject will be asked to complete two separate questionnaires at baseline prior to use of the remote monitoring system and again at completion of the study. The first questionnaire is the Self-Care of Heart Failure Index (SCHFI), and the second is the Minnesota Living with Heart Failure Questionnaire (MLHFQ), which are validated tools for quantifying self-care and quality of life.

The SCHFI is comprised of three subscales: self-care maintenance (choice of behaviors used to maintain physiologic stability), self-care management (response to symptoms when they occur) and self-care confidence. The maintenance, management, and confidence subscales are comprised of 5, 6, and 4 Likert questions, respectively. A higher score on the SCHFI indicates improved self-care.

The MLHFQ consists of 21 questions that use a 6-point Likert scale. The physical dimension score for the MLHFQ is the summation of 8 questions (e.g., Did your heart failure make you sit or lie down to rest during the day?), while the emotional dimension score is the summation of 5 other questions (e.g., Did your heart failure make you worry?). A lower score on the MLHFQ indicates higher quality of life.

#### **4.7.3 Health Literacy Evaluation**

One question regarding health literacy will be included in the questionnaire assessment. See Appendix 15.6.

### **5.0 Subject Selection, Enrollment and Withdrawal**

This protocol will accrue 304 subjects hospitalized with a primary or secondary diagnosis of ADHF. These subjects will then be enrolled and randomized to receive either standard care or to the intervention group (Tele-HC model) to assess the impact of the intervention on 60 day all cause readmission rates.

Definition of ADHF: One or more of these symptoms: shortness of breath, orthopnea or edema AND may have one or more of these signs: rales, peripheral edema, ascites, or pulmonary vascular congestion on chest radiography

#### **5.1 Inclusion Criteria**

- Hospitalized with primary or secondary diagnosis of ADHF (one or more of these symptoms: shortness of breath, orthopnea or edema AND may have one or more of these signs: rales, peripheral edema, ascites, or pulmonary vascular congestion on chest radiography)
- Adult patients >18 years old

#### **5.2 Exclusion Criteria**

- Overall life expectancy < 2 months
- Known skin allergy to adhesives (hydrocolloid, silicone, acrylic)

- Active systemic infection
- End stage renal disease (ESRD) on dialysis
- Subject or caregiver is not visually and tactile capable of smartphone and home device usage
- Inadequate cell phone coverage (including international patients or international travel during study period)
- Subject or legal guardian is not willing and able to provide appropriate informed consent

### **5.3 Subject Recruitment, Enrollment, and Screening**

Eligible subjects will be enrolled and randomized ~~prior to hospital discharge~~ to either remote monitoring or standard care. After randomization, participants will be remotely monitored for 60 days. Standard care will be per published guidelines (ACC/AHA HF guidelines). At these evaluations, routine and clinically-indicated investigations will include history and assessment of NYHA class, ECG, and blood work, as deemed appropriate by the clinician. Data from any clinical visits & assessments will be collected. Medication compliance will be assessed and adjustments in management made in accordance with individual subject needs as per the judgment of care providers. Rate of ER visits, hospital admissions, episodes of contact with health care providers, and mortality data will be collected by research assistants working with the clinical electronic medical record (EMR) and entered into Medidata Rave® for subsequent analysis. If the subject's primary provider requests information while the subject is on the study, identifiable information will be released to them for clinical care. Specifically, information regarding their ECG, weight, and overall health related to their heart failure.

#### Study Completion

A subject will be considered to have completed the study if he or she completed all assessments and procedures during the baseline and follow-up period of 60 days for primary endpoint events. All randomized patients will have a follow-up assessment at 30 and 60 days to determine survival status and hospitalization data. If the subject dies during this period, the study coordinator and/or PI should make every effort to obtain details of the subject's death from the relevant hospital or subject's physicians and/or relatives. If confirmation of death is not available through these mechanisms, the study coordinator and/or PI will attempt to confirm the subject's death through a death index search.

#### Study Withdrawal

If the subject dies after being randomized but prior to hospital dismissal, the subject will be withdrawn from the study.

If the subject is lost to follow up, every effort will be made to contact the subject and determine the reason that will then be documented, including the measures taken to follow-up. If subject withdraws or drops out of the study, the reason for withdrawal from the study is to be documented on the case report form (CRF) and in the source document. The study coordinator or investigator must attempt to document re-hospitalization data unless the subject expressly refuses to provide this information.

#### Treatment discontinuation

Subjects who terminate the use of the BodyGuardian® device will continue to be followed. Interruption of the BodyGuardian® device will not be considered treatment discontinuation.

## 6.0 Study Procedures

### 6.1 Study Schedule

Data Collection	Screening through 2 working days post hospital dismissal	Follow-up Visits	
		30 Days (-2/+7 days)	60 Days (+/- 14 days)
Informed Consent/Assessment of Eligibility	X		
Randomization	X		
Demographics/Medical History	X		
Medications	X	X	X
ECG (within 2 weeks)	X		
6 minute walk (to be taken from medical record if done)	X		X
Blood work (Creatinine, Hb, potassium, sodium, GFR)	X		
Ejection fraction (within 6 months)	X		
Home visit (BodyGuardian® implementation, medicine	X 		

reconciliation, nutrition review) 			
Self-Care of Heart Failure Index (SCHFI) 	X 		X 
Minnesota Living with Heart Failure Questionnaire (MLHFQ)	X 		X 
New York Heart Class	X		X
Health Literacy Measure	X		
Medical Outcomes General Adherence Measure (PHQ9)	X		
Subject training	X		
Follow-up outcomes/study endpoint events		X	X

*Intervention Arm only*

*The purpose of these measures is to summarize participant characteristics that may relate to later adherence behaviors (e.g., wearing the monitor and measuring body weight as instructed). The participant data will also be used to provide further context to qualitative interview data.*

